2. PARTICIPANT SELECTION

All subjects will be selected from the patient population at the investigational site. The investigator may review their records for subjects who meet the inclusion / exclusion criteria. Subjects may be qualified by telephone for their interest and availability for this trial. Subjects may be told that they will be trial fitted with a soft multifocal contact lens. If subject(s) can be successfully fitted and meet all inclusion / exclusion criteria, they may be dispensed to wear test lenses for daily wear, and return for a follow-up visits at approximately 2 ± 1 days, and 5 ± 3 days before being crossed over to the next lens.

The Informed Consent **MUST** be completed for each subject prior to enrollment.

A. Inclusion and Exclusion Criteria

Inclusion Criteria

Subjects must satisfy the following conditions for inclusion in the trial:

- Be of legal age, 18 years old or older
- Sign written Informed Consent.
- If a current contact lens wearer, usually wears their contact lenses for daily wear only.
- Have acceptable or optimal fit with test and control lenses and be willing to wear these lenses as directed for the duration of the study.
- Be correctable to high contrast Snellen distance VA to 20/25 in each eye.
- On examination, have ocular findings considered to be within normal limits.
- Normal binocularity (no amblyopia or strabismus, and no anisometropia of greater than 2.00D)
- Refractive astigmatism ≤ 1.00 diopters.
- Be willing and able to follow instructions and attend the schedule of follow-up visits.
- If not a current contact lens wearer, must have worn contact lenses previously and discontinued wear for reasons other than discomfort or dryness.
- For presbyopic performance study, need a reading add of +1.00 to +3.50 (inclusive).
- For presbyopic performance study, testing of EDOF curve, subject must have 20/50 or worse

distant corrected near visual acuity.

Exclusion Criteria

Any of the following will exclude a subject from this trial:

- Requires concurrent ocular medication contraindicating lens wear.
- Eye injury or surgery within twelve weeks immediately prior to enrollment for this trial.
- Pre-existing ocular condition that would contraindicating lens wear.
- Currently enrolled in an ophthalmic clinical trial.
- Pregnant, lactating or planning pregnancy (self-reported)
- Evidence of systemic or ocular abnormality, infection or disease likely to affect successful wear of contact lenses or use of their accessory solutions.
- Allergy or sensitivity to any product used in this trial.
- Any systemic disease including autoimmune disease, immunocompromising diseases, connective tissue disease, clinically significant atopic diseases, insulin dependent diabetes, use of medications including corticosteroids and antimetabolites that may affect the eye or be exaggerated by wearing contact lenses.
- Strabismus, amblyopia or habitually uncorrected anisometropia $\geq 2.00\text{D}$ Subjects who have undergone corneal refractive surgery
- Subjects with keratoconus or severe corneal irregularity contraindicating lens wear
- Inability to wear contact lenses, or an unacceptable contact lens fit
- Poor or unacceptable fit with any study lens
- Mesopic pupil size $< 3.00 \text{ mm OU}$ (measured at approx. 10 cd/m^2)
- Subjects who normally wear toric, GP, or hybrid contact lenses.
- Subjects who have never worn contact lenses will be excluded from this trial.
- Subjects who have previously worn contact lenses but discontinued wear due to discomfort or dryness related issues will be excluded from this trial.

B. Gender

Equal inclusion of both men and women in this study is desired but not necessary. There is no reported difference in contact lens safety or performance based on gender.

Pregnant women will be excluded from but women of childbearing potential, however, will not be excluded.

C. Racial/Ethnic Origin

There are no racial/ethnic enrollment restrictions. The racial/ethnic distribution of the participants will be likely reflecting the ethnic/racial population of the study site(s).

D. Vulnerable Populations

VTI employee may enroll in this study. Employees will be made aware that their decision of whether to participate will not affect their employment.

E. Age

The lens performance characteristics being tested during the study may results in age bias.

Example 1: Presbyopia typically occurs after 40 years old¹⁵. If we want to test the lens' Extended Depth of Focus performance, we will need to test it on moderate to mature presbyopic population, hence an older subject population.

Example 2: the Progressing Myopia typically shows up in early childhood, and progressively stabilizes in

early adulthood (usually 18-25 years of age).^{1,2} If we want to test the lens' ability to improve accommodative lag (a risk factor for myopia progression), we will recruit a younger population as accommodation decrease drastically after 30 years old.¹⁶

F. Total Number of Participants to be Enrolled

Up to a maximum of 600 subjects will be seen under this protocol. No more than 100 subjects will be enrolled at each site.

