1. INTRODUCTION

Visioneering Technologies, Inc. (VTI) currently has a market cleared multifocal contact lens NatrualVue Multifocal (NVMF), which is a Class II, non-significant risk (NSR) device. This contact lens product is designed for the correction of ametropia including myopia, myopia progression control (outside the US), hyperopia, and/or presbyopia. The optical design of the contact lens creates an enhanced depth of focus (EDOF), which provides clear distance, intermediate, and near vision. This unique optic while expands the depth of the focus, it also generates a significant amount of myopic defocus on the retina in a gentle and discrete way, therefore, it causes minimal visual disturbance.

A. Type of Research

Clinical study for NSR device refinement. This will be a single-masked trial. Subjects will be masked to the design or brand of lenses.

B. Purpose/Objective of the Study

Under this protocol, clinical trials will be undertaken to further optimize the current product design, and evaluate the design with different power or lens configurations including multifocal-toric lenses or other market approved lens materials. The goal of these Research and Development studies is to expand the product line in order to address and serve a larger population.

This protocol will serve as an umbrella protocol, as the clinical studies will be focusing on different aspects of lens performances during difference phase of product development and may conduct at different clinical sites. Minor optimization to the lens design will be made in Phase I, at this phase, shorter follow up evaluations will be made. Other available lenses or lens materials may be used for bench marking purposes. After optimization, the lenses may be dispensed for longer term performances (Phase II).

For each clinical site, the investigator required information (CV, license, site questionnaire, letter of submission) would be submitted to the IRB for review prior to that site recruiting or enrolling subjects. For the duration of the study during dispensing trials, subjects will be required to wear the study lenses for a minimum of 6 hours per day, 5 days per week. Subjects will not be allowed to keep the lenses.

C. Background of the Study

C.1 Normal Vision

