VTI lenses are molded, hydrated and sterilized at an FDA inspected and audited facility (Pegavision Corporation, Taiwan). The VTI lens design has received FDA 510k clearance (K150385, 2015, Visioneering Technologies, Inc.). Minor optimization to the lens design will be made (phase I), to include base curves, power profiles, optical zone diameters, edge design, front surface design, toric design and contact lens material performance. None of these minor changes to the design are anticipated to impact the safety and efficacy of the product. After optimization, the lenses will be compared to other available multifocal contact lenses (Phase II).

VTI lenses are of an FDA approved etafilcon-A material, other materials to be evaluated will either be cleared by FDA or passed material safety evaluations per FDA contact lens guidance. The lenses will only be worn on a daily wear basis. All other brands of lenses used will be FDA approved/cleared and will also only be worn on a daily wear basis. If a comparative product is not FDA approved/cleared, separate IRB approval for the use of such product will be required. All lenses will be fitted according to the manufacturer recommended fitting guides, and only those subjects displaying the characteristics of an acceptable lens fit will be dispensed with the lenses.

Data collected under this protocol will include state-of-the-art evaluation methods in contact lens safety and performance testing, presbyopia performance testing and myopia progression control testing; including, but not limited to, vision performance under low-light, and low-contrast conditions, viewing distances or vergences, contrast sensitivity, stereopsis, lens fitting and surface assessments, ocular health and parameter assessments, refraction, and subjective evaluations.

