5. PARTICIPANT RECRUITMENT AND INFORMED CONSENT

A. Recruiting

Subjects will be recruited from participating clinic which provides contact lens services or within VTI. Employees will be made aware that their decision of whether to participate will not affect their employment.

B. Informed Consent / Assent

Written informed consent is required prior to enrollment in the study. It is the responsibility of the Investigator to obtain a valid Informed Consent.

C. Obtaining and Documenting Consent

The signed Consent is part of the study documents and will be kept by the investigator.

D. Participant Comprehension and Capacity

The investigator or the authorized study personnel will assess the participant has clear understanding on all the information presented in the Consent prior to the document being signed.

E. Costs to Participants

There will be no study associated costs to the subjects.

F. Compensation to Participants

Subjects will be compensated for their time while participating in the study with gift certificates/checks.

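### Do sponsor employees as subjects, with no rule for their data, undermine a comparison of the sponsor's lens with another brand?

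*Combined protocol and SAP*

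**What the plan says.** Three places in the combined protocol and SAP bear on where subjects come from.

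- Section 2, opening paragraph: "All subjects will be selected from the patient population at the investigational site".
- Section 2.D (Vulnerable Populations): "VTI employee may enroll in this study".
- Section 5.A (Recruiting): "Subjects will be recruited from participating clinic which provides contact lens services or within VTI".

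The only provision specific to employees concerns voluntariness: "Employees will be made aware that their decision of whether to participate will not affect their employment". It appears in both 2.D and 5.A. The eligibility criteria in 2.A do not mention employment.

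On protection against response bias, section 1.A says "Subjects will be masked to the design or brand of lenses". Section 3.A repeats subject masking for Phase I and describes Phase II as masked crossover trials.

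On comparators, section 1.B says "Other available lenses or lens materials may be used for bench marking purposes". Section 1.C.4 expects a Phase II comparison with other multifocal lenses on the market. Section 3.A is looser: the comparison may be with other sponsor designs, with other available lenses, or with both.

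Section 3.B is two sentences long. It provides for descriptive statistics and, where control-lens data exist, suitable inferential comparisons. It defines no analysis population and has no rule for employees.

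**The concern.** Two things look wrong at first reading.

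One is textual. If every subject is a patient of the site, an employee recruited inside the sponsor has no place in the trial, yet two other sections admit such a person.

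The other is statistical. An employee of the company that makes one of the lenses may want that lens to do well. Many of the outcomes are subject responses: acuity, glare, distortion, and the vision and comfort questionnaire. The list of outcomes in 3.A calls questionnaires optional, but the methods list, also in 3.A, includes this one without the optional or as-needed tag that several other items carry, so it should be counted as exposed. A crossover removes a tendency to answer generously about both lenses; it does not remove a preference for one of them. With no stated rule, a reader of a brand comparison could not tell whether the result depended on employees.

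At stake would be the validity of any claim that the sponsor's lens outperforms, or matches, a competitor on subject-reported or subject-performed measures.

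**Working it through.** **Step 1. Is there a contradiction about eligibility?** Set side by side, section 2 says site patients, 2.D says employees may enrol, and 5.A says clinic or sponsor. The two sections that name employees agree with each other, no criterion excludes them, and an employee who is also a patient of the site satisfies all three. What remains is that the word for all subjects in section 2 is too broad. The conflict is over recruitment source and affects no estimate or test.

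**Step 2. What must happen for bias to arise?** Four conditions must hold together: a comparison with another brand is run; the outcome is a subject response; some employees become unmasked; and those employees shift their responses in favour of one lens. The first is optional under 3.A. The documents give no sign of the third and nothing on the fourth.

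**Step 3. How large would it be?** The plan states no significance level, standard deviation, sample size for a comparison or employee share, so there is no figure to reproduce. The following is illustration on assumed inputs.

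- Paired comparison, true lens difference 0, SD of the within-subject difference set to 1, two-sided level 5%.
- p = share of subjects who are unmasked employees; b = their shift in SD units; both assumed.
- n = 100, borrowed from section 2.F ("No more than 100 subjects will be enrolled at each site"). This is an enrolment ceiling, not a planned comparison size. n = 30 is an assumed smaller study.

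Bias = p × b. The false-positive rate comes from the noncentral t distribution with n − 1 degrees of freedom and

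ncp = p·b·√n / √(1 + p(1 − p)b²).

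Example, n = 100, p = 0.20, b = 0.5: bias = 0.10; ncp = 0.10 × 10 / √(1 + 0.16 × 0.25) = 1 / √1.04 = 0.981; rate 16.3%.

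| n | b | p = 5% | p = 10% | p = 20% | p = 50% |
|---|---|---|---|---|---|
| any | 0 (masking holds) | 5.0% | 5.0% | 5.0% | 5.0% |
| 100 | 0.25 | 5.2% | 5.7% | 7.8% | 23.3% |
| 100 | 0.50 | 5.7% | 7.8% | 16.3% | 67.1% |
| 30 | 0.50 | 5.2% | 5.8% | 8.1% | 25.0% |

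At b = 0.5 the rate reaches 10% at a share of about 13% with n = 100, or about 25% with n = 30. If employees are 20% of subjects but only half of them become unmasked, p is 0.10 and the rate is 7.8% (n = 100).

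**Step 4. What would excluding employees cost?** If a share p of all subjects are employees and non-employees form the main analysis, its interval widens by 1/√(1 − p) − 1:

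- 5%: 1/√0.95 − 1 = 2.6%
- 10%: 1/√0.90 − 1 = 5.4%
- 20%: 1/√0.80 − 1 = 11.8%
- 50%: 1/√0.50 − 1 = 41.4%

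With the t quantile updated as well, n = 30 and a 20% share leave 24 subjects, and the widening is (2.069/√24) / (2.045/√30) − 1 = 13.1%. At a 50% share with n = 30 it is 48%. This cost is incurred whether or not masking holds.

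**The case for a change.** The strongest case for a change is this. Masking is the only named protection, and the protocol does not describe how it is kept up when lenses are dispensed for subjects to take away. Employees of the lens maker are the group for whom relying on masking alone is hardest to defend. Nothing caps their share, so the harmless range in the table is not guaranteed. Section 3.B is silent, and a choice made after the data are seen, in either direction, would look selective. The remedy would cost a few lines of text and at most one case report form field.

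Much of this stands as description. The omission is real, a lens-specific preference would survive the crossover, and a 20% share with a half-SD shift at n = 100 would matter.

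It does not carry the conclusion, for three reasons. First, the chain from omission to bias passes through unmasking, which the plan sets out to prevent and which no document suggests will fail. Second, 3.B defines no population for anyone, so the missing employee rule is one part of a brief analysis section and not a separate defect. Third, making non-employees the main analysis is open to fair debate: it removes eligible, masked subjects for a bias not shown to exist. An all-subject main analysis, with results also shown without employees, would tell a reader just as much and would not widen the main interval. An analyst can do that without a change to the plan, provided employment status is on record. The case report forms are held separately (section 3.D) and may already capture it.

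**Conclusion.** No change is needed. The inconsistency between the opening of section 2 and sections 2.D and 5.A is a clerical slip over recruitment source; employees are eligible on any reading of the sections that mention them. The silence in 3.B is a gap that an analyst can fill sensibly by keeping all subjects and checking the result without employees.

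Followed as written, with masking intact, the false-positive rate stays at 5.0% whatever the employee share. At shares of unmasked employees up to 10%, the illustrated rates run from 5.2% to 7.8%. The 67.1% figure needs half of all subjects to be unmasked employees with a half-SD shift, which nothing in the documents suggests.

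This rests on subject masking working as planned and on employees being a minority in any brand comparison. The documents confirm the intention to mask but say nothing about the share. Evidence of widespread unmasking, or a brand comparison run mostly on employees, would reopen the question.

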3. STUDY DESIGN / METHOD / PROCEDURES

A. Summary of the Research Design

The lens optimization trials (Phase I) will involve both non-dispense and dispensing clinical trials. These trials will be prospective and single masked (subject). After an optimized design is determined, the lenses will be dispensed in prospective, masked, cross over trials comparing the lenses to other optimized VTI lens designs and/or to other available contact lenses (Phase II). Phase II trials could be a dispensing study for a period of 1 week each. There will be a follow-up visit during the trial at approximately 2 ± 1 days, and 5 ± 3 days.

All lenses will be dispensed for **daily wear** in this trial.

All data for this trial will be collected using CRFs that will be supplied by the sponsor.

Non-Dispensing Visits	Procedures	Data Collection
Enrollment	
• Biomicroscopic examination.• Baseline ocular health and visual performance evaluations.	
• Subject reads and signs Informed Consent.• Baseline Form
Lens Fitting & performance evaluations (Lens 1)	
• Biomicroscopic examination (if not on the same day of enrollment).• Trial fit lenses.• Visual performance evaluations with lens	
• Lens Evaluation Form• Visual performance Form
Lens Fitting & performance evaluations (Lens 2)	
• Biomicroscopic examination (if not on the same day of enrollment).• Trial fit lenses.• Visual performance evaluations with lens	
• Lens Evaluation Form• Visual performance Form
Exit visit	
• Collect data for End-of-day visit/Trial Exit.	
• Lens End-of-day Visit Form/Trial Exit Form
Unscheduled Visit	
• Clinical exam as necessary	
• Unscheduled Follow-up Visit Form.• Trial Exit Form, as necessary.• Potential Adverse Event Form, as necessary.

Dispensing Visits	Procedures	Data Collection
Fitting / dispensing visit	
• Biomicroscopic examination.• Trial fit lenses.• Dispense lenses.	
• Subject reads and signs Informed Consent.• Baseline Form• Lens Dispense Evaluation
2-Day Follow-up Visit (2 \pm 1 days)	
• Collect data for 2 Day visit.	
• Lens 2-day Visit Form
1-Week Follow-up Visit (5 \pm 3 days)	
• Collect data for 1-Week visit.• Collect data for Trial Exit.	
• Lens 1-Week Visit Form• Trial Exit Form
Unscheduled Visit	
• Clinical exam as necessary	
• Unscheduled Follow-up Visit Form.• Trial Exit Form, as necessary.• Potential Adverse Event Form, as necessary.

Scheduled Visits

There are three scheduled visits per lens for a dispensing trial:

- Enrollment / dispensing
- Follow-up visit at 2 \pm 1 day
- Follow-up visit at 5 \pm 3 days.

Unscheduled Visits

Visits that are instigated by the subject or requested by the investigator for health or vision-related reasons that occur between scheduled trial visits as specified above are classified as unscheduled visits. In addition, every visit after the trial period that is required because of a finding during the trial is considered an unscheduled visit. For every unscheduled visit the Unscheduled Follow-Up Visit Form must be completed and the reason for the unscheduled visit must be documented.

Missed Visits

Although every effort should be made to comply with the proposed visit schedule, in the event of a missed trial visit, the visit will be documented as missed on the appropriate CRF for that visit.

Exit Visit / Completion of trial

A Trial Exit Form will be completed when each subject completes the trial or is permanently discontinued from the trial. The form will detail the reason(s) for discontinuation.

Study Outcomes:

Performance outcomes:

- Lens fit (biomicroscopy/slit lamp evaluation)
- Other visual acuity tests may include
 - a. Best spherically corrected
 - b. High and low contrast
 - c. Photopic and mesopic
 - d. Distance, intermediate and near
 - e. Extended Depth of Focus (EDOF) curve (+2D to -4D)

- Contrast sensitivity (optional)
- Glare or visual distortion (optional)
- Accommodation performance (optional)
- Questionnaires (optional)

Safety outcomes:

- Best Corrected Visual acuity (High contrast),
- Corneal health as assessed by slit lamp biomicroscopy and other signs and symptoms
- Adverse events

Study Procedures:

Study Treatment

The study method is comprised of the placement of lens(es) on the eye.

Methods:

1. Following detailed explanation and signing an informed consent form, each subject will perform the following:
 - a. Baseline measurements on visual acuity (Best Corrected Visual Acuity), corneal health, ocular surface topography and anterior segment examination. If the subject meets this study's enrollment criteria,
 - b. The study lens will be placed on the eye.
 - c. The subject will undergo the following evaluations:
 - i. Lens evaluation
 1. Lens position and movement
 2. Surface wettability evaluation (as needed)
 3. Slit lamp fluorescence imaging (as needed)
 4. Tear Exchange evaluation (as needed)
 - ii. Photography/videography from anterior segment examination or lens evaluation (as needed)
 - iii. Vision and Comfort assessment (questionnaire)
 - iv. Uncorrected distance visual acuity (UCVA)
 - v. Habitual distance visual acuity (as needed)
 - vi. Distance best corrected visual acuity (BCVA)
 - vii. Other visual acuity tests may include
 1. Best spherically corrected
 2. Low contrast letters

3. Mesopic lighting conditions
4. Intermediate and near viewing distance
5. Extended Depth of Focus (EDOF) curve (+2D to -4D)

- viii. Glare testing (as needed)
- ix. Distortion test (as needed)
- x. Contrast Sensitivity (optional)
- xi. Add power determination (optional)
- xii. Accommodation range (optional)
- xiii. Accommodative lag (optional)

- d. The lens will be removed at the end of evaluation. Biomicroscopy and BCVA will be conducted as safety monitoring procedures.

All above mentioned testing are either standard clinical test in a routine eye exam or typical clinical/vision research evaluation method.

B. Analysis of Study Results

Descriptive statistics will be calculated for the primary variables in this trial. Where data from control lenses are available, appropriate inferential comparisons will be made.

C. Monitoring

VTI may provide a monitor who will monitor according to Good Clinical Practices (GCPs) the administrative (enrollment, discontinuations, etc.) and safety aspects (incidence and severity of complications, etc.), verify data integrity and assure the continued protection of subjects' rights and welfare.

D. Storage of Data

Case Report Forms (CRFs) are provided separately from this clinical protocol document. CRFs will be filled out legibly and completely (black or blue ball point pen). The original and copy of CRFs will be kept by the investigator. The CRF and related clinical files should be stored at least two years after the study is completed.

The sponsor will store study data electronically. Only authorized personnel have access to the study data.

E. Confidentiality of Data

The anonymity of participating subjects must be maintained. Subjects are identified by their initials and assigned a subject identification number on CRFs and other documents. Documents not submitted that identify the subject (e.g., the signed informed consent document) must be maintained in strict confidence by the investigator.

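### Does comparing lenses wherever control-lens data exist, when glare and distortion are tested only as needed, bias the comparison through selective testing?

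*Combined protocol and SAP*

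**What the plan says.** All references are to the combined protocol and SAP.

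- **Section 3.B, Analysis of Study Results**, has two sentences: "Descriptive statistics will be calculated for the primary variables in this trial", and "Where data from control lenses are available, appropriate inferential comparisons will be made". No primary variable is named, and no test, analysis set or missing-data rule is given.
- **Section 1.C.4** describes the measurements of the programme as a whole: "Data collected under this protocol will include state-of-the-art evaluation methods", with a non-exhaustive list that contains "contrast sensitivity, stereopsis, lens fitting and surface assessments".
- **Section 3.A, Study Outcomes**, is permissive. Acuity testing is introduced by "Other visual acuity tests may include", and contrast sensitivity, glare or distortion, accommodation and questionnaires are each marked optional.
- **Section 3.A, Study Procedures, Methods 1.c**, opens with "The subject will undergo the following evaluations". Glare and distortion are tagged as needed there, contrast sensitivity and the accommodation tests optional, and the vision and comfort questionnaire has no tag.
- **Section 1.A** states masking of subjects only.

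**The concern.** Read literally, section 3.B makes the availability of control-lens data the only condition for a between-lens test. If the as-needed tag is a decision about the individual subject, an examiner who may know which lens is on the eye controls what data become available. Subjects who complain would be the likeliest to be tested, so those with glare scores would be the worse-scoring ones. Two distortions could follow. A real difference between lenses would shrink, because both tested groups are drawn from the bad end of the scale. And a lens on which examiners test more readily would look better than it is, because its tested group includes milder cases.

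Glare and distortion bear directly on the claim in section 1 that the optic disturbs vision little. The disagreements between the lists add to the worry: a reader cannot tell from the protocol alone which outcomes every subject contributes.

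**Working it through.** **1. The lists side by side**

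| Outcome | 1.C.4 | 3.A Study Outcomes | 3.A Methods 1.c |
|---|---|---|---|
| Contrast sensitivity | listed | optional | optional |
| Stereopsis | listed | absent | absent |
| Questionnaire / subjective evaluation | listed | optional | no tag |
| Glare, distortion | not named | optional | as needed |
| Low-contrast and mesopic acuity | listed | permissive | permissive |

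Section 1.C.4 covers safety, presbyopia and myopia-control work together and says its list is not exhaustive. A programme-wide list is compatible with items being optional in any one study. What is left is a stereopsis entry without a procedure, a questionnaire tagged in one place and not the other, and two different tags for glare and distortion. These are editorial.

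**2. What the selection argument needs**

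It needs (i) testing decided per subject and per lens, and (ii) a decision related to how bad the vision is. No section states either. Evidence on (i):

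- Section 1.B calls this an umbrella protocol whose studies look at different aspects of lens performance.
- Section 2.A has criteria that apply only to presbyopic studies. Section 2.E chooses the population according to which test a study is about: an older one for depth of focus, a younger one for accommodative lag.
- The non-dispensing visit table in section 3.A gives Lens 1 and Lens 2 identical procedures and the same forms.
- Section 3.D says case report forms are supplied separately and completed in full. They could fix the tests for each study.
- Section 1.B says other lenses may be used for benchmarking, so not every study has a control. The availability condition in 3.B most naturally means studies that have one.

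**3. Size if both conditions held**

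The documents give no testing rate, SD or expected difference, so there is no figure of the plan's own to reproduce. Every input here is assumed. Let the score be N(0,1) on the control lens and N(d,1) on the other, higher being worse. A wear is tested when a prompt with correlation r to the score exceeds c. With λ(x) = φ(x)/[1 − Φ(x)],

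expected difference among those tested = d + r[λ(c − rd) − λ(c)].

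Take d = 0.5 and 30% of control-lens wears tested, so c = 0.524 and λ(c) = 1.159:

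- r = 0: 0.500, no loss
- r = 0.2: 0.5 + 0.2(1.086 − 1.159) = 0.485, loss 3%
- r = 0.5: 0.5 + 0.5(0.980 − 1.159) = 0.411, loss 18%
- r = 0.7: 0.5 + 0.7(0.912 − 1.159) = 0.327, loss 35%
- r = 1.0: 0.5 + 1.0(0.814 − 1.159) = 0.155, loss 69%

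Phase II is cross-over, so the natural contrast is within subject. Simulating subjects tested with both lenses (between-lens correlation 0.5 for score and prompt) gives losses of about 12%, 23% and 46% for r = 0.5, 0.7 and 1.0.

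With no true difference but 50% tested on one lens and 30% on the other, the false difference is r[λ(0) − λ(0.524)] = r(0.798 − 1.159) = −0.181, −0.253 and −0.361 SD for r = 0.5, 0.7 and 1.0. Among subjects tested with both lenses it is about −0.12, −0.17 and −0.24 SD.

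If a study either tests every subject with every lens or omits the test, all of these are zero.

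**The case for a change.** The strongest case for a change is textual. The procedure list applies to each subject and uses two different tags. If both meant a choice made per study, one tag would have been enough. Other as-needed items in the same list, such as photography or habitual acuity, read easily as decisions about the person in the chair. No section says when a test is needed, who decides, or that it must be done with both lenses, and examiner masking is not stated. The arithmetic is sound, and restricting to subjects tested with both lenses reduces the bias without removing it. It also leaves few subjects: with 30% tested per lens and a between-lens correlation of 0.3 to 0.7, only 13% to 19% have both results.

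What stands is that the text does not settle the level at which the tag applies, that the lists are uneven, and that no primary variable is named. What does not stand is the step from there to a biased analysis. That requires a symptom trigger that no section states, and the per-subject reading is no better supported than the per-study one. The calculation sizes a scenario the plan does not describe.

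**Conclusion.** The concern does not call for a change. The selection bias is possible in principle, but it depends on two unstated conditions. Its size runs from zero to large according to inputs the documents do not supply: the loss on a 0.5 SD difference with 30% tested is 0% at r = 0, 3% at r = 0.2 and 69% at r = 1.0, or about 46% at r = 1.0 for subjects tested with both lenses. On the reading that the umbrella design and the identical lens-by-lens visit schedule support at least as well, it is zero.

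The remainder is missing detail: which tests a given study runs, which variable is primary, and a few mismatched tags. Study-level forms and analysts would ordinarily settle these. An analyst who found glare scores on only some subjects, and on different subjects for each lens, would see that from the counts and would not treat them as a cross-over comparison. Choosing one acuity measure or visit as primary for every Phase II study would be a preference, since section 3.A says only that Phase II studies could be dispensing ones, so the follow-up visits need not exist.

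This conclusion assumes that the study-level forms, which are not part of the documents, fix the tests for each study. Forms that left glare or distortion testing to an examiner's judgement for individual subjects, followed by a formal comparison of lenses on those results, would reopen the point.
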